Subjects. After obtaining their written informed consent, men and post-menopausal women aged 40-79 yrs with stage IIIb and stage IV CKD (eGFR 15-45 mL/min/1.73m²) and normal or modestly elevated serum phosphorus (2.8-5.5 mg/dL) will serve as subjects. Patients will undergo screening for eGFR and phosphorus at the UPI Building to determine study eligibility. Estimated GFR will be calculated using the 4-variable MDRD prediction equation ⁵⁷. Major inclusion/exclusion criteria are presented below:

Inclusion Criteria:

- 1) Aged 40-79 yrs; women must be post-menopausal (serum phosphorus increases after menopause in women ⁵⁸)
- 2) CKD stage IIIb or IV (eGFR with the 4-variable MDRD prediction equation: 15-45 mL/min/1.73m²; stable renal function in the past 3 months)
- 3) Baseline serum phosphorus 2.8-5.5 mg/dL (stable in the past 3 months); not taking phosphate binders
- 4) Serum albumin concentration >3.0 g/dL
- 5) Mini-mental state examination (MMSE) score of ≥ 24 (cognitive function screening); ability to provide informed consent

Exclusion Criteria:

[figure not shown]
- 1) Patients with advanced CKD requiring chronic dialysis
- 2) Patients at high risk for gastrointestinal events or alterations in gastrointestinal anatomy(e.g., history of gastrointestinal surgery, colon cancer), hypomotility disorders (e.g., constipation, ileus), current bowel obstruction, or fecal impaction
- 3) Significant co-morbid conditions that lead the investigator to conclude that life expectancy is less than 1 year
- 4) Expected to undergo living related transplant in next 6 months
- 5) History of severe congestive heart failure (i.e., EF < 35%)
- 6) History severe liver disease
- 7) Hospitalization in the past 3 months
- 8) BMI ≥ 40 kg/m² (FMD measurements can be inaccurate in severely obese patients)
- 9) Taking medication(s) that interact with agents administered during experimental sessions (e.g., sildenafil interacts with nitroglycerin)
- 10) Active vitamin D analogue use (i.e., calcitriol, paricalcitol, doxercalciferol)
- 11) Alcohol dependence or abuse
- 12) Current tobacco abuse
- 13) Use of prednisone and other immune suppressant medications

C. Study Design and Research Methods

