1. Completed prospective, randomized, placebo-controlled double-blind trial, Phosphorus Lowering to Treat Vascular Dysfunction in Chronic Kidney Disease (COMIRB #13-0328) or willing to participate in 12-week run-in period
2. Aged 40-79 years; women must be post-menopausal (serum phosphorus increases after menopause in women⁵⁸)
3. CKD stage IIIb or IV (eGFR by 4-variable MDRD prediction equation: 15-45 mL/min/1.73m²); stable renal function in the past 3 months
4. Mini-mental state examination (MMSE) score ≥24 (cognitive function screening); ability to provide informed consent

Exclusion Criteria:

1. Subjects with advanced CKD requiring chronic dialysis
2. Subjects at high risk for gastrointestinal events or alteration in gastrointestinal anatomy (e.g., history of gastrointestinal surgery, colon cancer), hypomotility disorders (e.g., constipation, ileus), current bowel obstruction, or fecal impaction
3. Significant co-morbid conditions that lead the investigator to conclude that life expectancy is less than 1 year
4. Expected to undergo living-related kidney transplant in the next 6 months
5. History of severe congestive heart failure (i.e., EF < 35%)
6. History of severe liver disease (i.e., elevated bilirubin, AST, ALT, or evidence of liver cirrhosis on biopsy or imaging)
7. Hospitalization in the past 3 months
8. BMI ≥40 kg/m² (FMD measurement can be inaccurate in severely obese subjects)
9. Active vitamin D analogue use (i.e., calcitriol, paricalcitol, doxercalciferol)
10. Alcohol dependence or abuse (i.e., as documented in subject's chart per PCP or mental health provider or if stipulated by subject)
11. Current tobacco abuse (i.e., current and habitual use of any tobacco product)
12. Use of prednisone and other immune suppressant medications (i.e., current and ongoing use of prednisone or other immune suppressant medication)

A Standard Operating Procedure is in place that prohibits the use of nitroglycerin (NTG) in subjects with systolic blood pressure <100 mmHg and with migraine headache. Additionally, it is part of the Standard Operating Procedure that subjects are educated regarding drugs that interact with lanthanum carbonate (levothyroxine, quinolone antibiotics, and other cationic medications) and are instructed in correct timing of lanthanum carbonate administration with respect to drugs that interact with it.

[figure not shown]
C. Study Design and Research Methods

[figure not shown]

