 - Receive polyethylene glycol 1 g PO TID with meals as a stool marker
 - Submit 1 stool specimen prior to initiating polyethylene glycol to be used as a comparison
- **Session 3:** End of Phosphorus Balance Study
 - 48-hour admission to CTRC
 - Blood sampling to monitor serum phosphorus concentration, serum creatinine for measurement of kidney function, and evaluation of markers of mineral metabolism
 - 24-hour urine and stool collection for phosphorus and calcium measurement (2 will be collected)
 - Subjects will continue 1 g of polyethylene glycol with each meal as a non-absorbable stool marker during the CTRC inpatient admission.
 - Continue CTRC-prepared fixed low phosphorus diet
 - Continue current dose of lanthanum or placebo
 - Final FMD_{BA} measurement to be performed at the UPI Vascular Lab

Figure 1

[figure not shown]
For subjects not enrolled in the parent Phosphorus Lowering RCT:

- **Session 1:** Consent and screening measurements
- **Session 2:** Baseline measurements
 - Resting arterial blood pressure
 - Blood sampling to monitor serum phosphorus concentration, serum creatinine for measurement of kidney function, and evaluation of markers of mineral metabolism
 - FMD_{BA} (endothelium-dependent dilation)
 - Endothelium-independent dilation (EID) to sublingual nitroglycerin
 - Randomization to either lanthanum carbonate or placebo
- **Session 3-5:** Biweekly/monthly check-in (see below)
- **Session 6:** Beginning of proposed Phosphorus Balance study (*same as Session 2 for those recruited from parent Phosphorus Lowering RCT*)
 - Resting arterial blood pressure
 - Blood sampling to monitor serum phosphorus concentration, serum creatinine for measurement of kidney function, and evaluation of markers of mineral metabolism
 - FMD_{BA} (endothelium-dependent dilation) and endothelium-independent dilation (EID) to sublingual nitroglycerin
 - Receive CTRC-prepared fixed low phosphorus diet (daily breakfast, lunch, dinner, and a snack) including deionized water
 - Mifflin St. Jour equation and activity factor of 1.4 will be used to determine caloric needs. Based on their caloric needs, subjects will be assigned to one of four kilocalorie diet categories: 2000-2300, 2300-2600, 2600-2900, 2900-3200. The subjects will then select their meals from four different pre-set menus.
 - Macronutrients: 15% protein/ 30% fat/ 55% CHO \pm 2% for each macro

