a) Conduit artery vascular endothelial dependent dilation (EDD) and endothelial independent dilation (EID): Conduit artery EDD, brachial artery flow-mediate dilation (FMD_{BA}), will be determined using high-resolution ultrasonography (GE Vivid7 Dimension) as described originally by Celermajer et al.²⁹ and used recently by the co-mentor.^{31,32} ECG-gated end-diastolic ultrasound images and Doppler flow of the brachial artery will be acquired during baseline and FMD_{BA} conditions. For FMD_{BA} , reactive hyperemia will be produced by inflating a pediatric BP cuff around the forearm to 250 mmHg for 5 minutes followed by rapid deflation. Brachial artery endothelium-independent dilation (EID), an index of smooth muscle sensitivity to exogenous nitric oxide, will be determined by measuring brachial artery dilation for 10 minutes after administration of sublingual nitroglycerin (0.4 mg).^{32,33} A commercially available software package (Vascular Analysis Tools 5.8.1, Medical Imaging Applications) will be used to acquire ECG-gated brachial artery diameters. As recently recommended,³⁴ FMD_{BA} will be determined as the mm and % Δ from baseline diameter.³²⁻³⁴ Shear rate will also be calculated, and if group- or condition- differences exist, FMD_{BA} will be adjusted accordingly.³⁴⁻³⁶

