Risks of this procedure include: The assessment of FMD_{BA} is minimally invasive. Inflating the blood pressure cuff below the elbow during this procedure may cause a mild to moderate intensity “pins and needles or numbing” sensation that goes away as soon as the cuff is deflated. In addition, patients will receive a dose of sublingual nitroglycerin to measure EID, an essential control measure without which the results cannot be properly interpreted. Sublingual nitroglycerin is a medication with a rapid vasodilator effect and is routinely used in patients with coronary artery disease to help relieve chest pain. Side effects of sublingual nitroglycerin are short-lived (30-60 minutes). Approximately 60% of people who receive nitroglycerin will experience a headache. The subject may experience symptoms such as lightheadedness, and in rare instances (1 in 1000) lowered heart rate, which could lead to fainting. However, these risks are primarily when a person is upright, and subjects will be lying supine during administration of nitroglycerin. Finally, placing the pill under the tongue could cause irritation to the area in the back of the mouth. The subjects will be monitored by frequently asking about subjective complaints, as well as by frequent heart rate and blood pressure measurements (prior to and every 15 minutes after taking the medication for 1 hour). In addition, during the 10-minute period when brachial artery dilation to nitroglycerin is assessed (peak activity of drug), blood pressure and heart rate will be assessed every 2 minutes. In the rare case that blood pressure drops drastically, an intravenous catheter will be available for infusion of normal saline. Still, nitroglycerin has been administered safely for over a decade in the laboratory the co-mentor performed her doctoral training, as well as in other laboratories and in clinical situations worldwide. Per standard operating procedure, nitroglycerin will not be given to

any subject with a systolic blood pressure less than 100 mmHg on the day the measurements are performed, history of migraine headaches, or previous adverse reaction to administration.

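### The sub-study schedules nitroglycerin for run-in subjects but drops the main trial's exclusion for interacting drugs such as sildenafil, and no other stated rule replaces it

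*Combined protocol and SAP*

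**What the plan says.** The main protocol (section IV.B, Exclusion Criteria, item 9) excludes subjects "Taking medication(s) that interact with agents administered during experimental sessions (e.g., sildenafil interacts with nitroglycerin".

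The sub-study protocol takes subjects from two sources: those completing the main trial, and separately recruited subjects who go through a 12-week run-in on lanthanum or placebo. For the second group, section IV.C lists at Session 2 "Endothelium-independent dilation (EID) to sublingual nitroglycerin", and at Session 6 FMD "and endothelium-independent dilation (EID) to sublingual nitroglycerin". Section IV.D(a) sets the dose, with dilation measured for 10 minutes "after administration of sublingual nitroglycerin (0.4 mg" under the tongue).

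The sub-study states its limits on nitroglycerin in two places:

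- Below the exclusion criteria in section IV.B, a Standard Operating Procedure is said to be in place that "prohibits the use of nitroglycerin (NTG) in subjects with systolic blood pressure <100 mmHg and with migraine headache".
- The risk paragraph of section IV.D(a) repeats the pressure limit and adds "history of migraine headaches, or previous adverse reaction to administration".

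On drug interactions, section IV.B says that "subjects are educated regarding drugs that interact with lanthanum carbonate", and the safety measures in section IV.C space other drugs around lanthanum doses.

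**The concern.** Run-in subjects never pass the main trial's screening, so its exclusion 9 does not reach them unless the sub-study repeats it or carries it over. It does neither. The main protocol treats the interaction as reason enough to keep a person out, yet the sub-study schedules the same 0.4 mg dose for newly recruited people with no such screen stated.

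What is at stake is subject safety. The precautions in section IV.D(a) are supine dosing, pressure and heart-rate checks every 2 minutes for 10 minutes and every 15 minutes for an hour, and an intravenous catheter at hand. They detect and treat a fall in pressure. They do not keep the dose from someone on an interacting drug, and a systolic cut-off of 100 mmHg does not identify such a person.

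**Working it through.** **Exclusion lists compared.** The main protocol has 13 items and the sub-study 12.

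| Main protocol item | Sub-study item |
|---|---|
| 1–8: dialysis, gastrointestinal risk, life expectancy, transplant, heart failure, liver disease, hospitalization, BMI | 1–8, same order |
| 9: drugs interacting with session agents | none |
| 10–13: active vitamin D, alcohol, tobacco, immune suppressants | 9–12, same order |

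Only item 9 is missing.

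**Whether item 9 was redundant.** It was not. The main protocol (section IV.D(a)) already had the pressure, migraine and previous-reaction limits. The sub-study kept those and lost the one rule aimed at interacting drugs.

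**Search for a substitute in the sub-study.**

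- Nitroglycerin limits (IV.B, IV.D(a)): pressure, migraine, previous reaction. No drug rule.
- Interaction text (IV.B, IV.C safety measures): lanthanum only.
- Patient stopping criteria, standard medical treatment and the statin rule (IV.C, IV.E): silent on nitrate interactions.
- Medical history (IV.C, Data Collection): described for subjects recruited for the main trial.
- Run-in Sessions 1, 2 and 6 (IV.C): no medication review listed.

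Taken together, a sildenafil user with systolic pressure of 100 mmHg or more, no migraine and no earlier reaction meets every written condition for dosing.

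**Subjects from the main trial.** They passed exclusion 9 at entry. Whether they receive nitroglycerin in the sub-study is unclear: their sessions list none, but run-in Session 6, which does, is labelled "same as Session 2 for those recruited from parent Phosphorus Lowering RCT".

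**Scale of exposure to nitroglycerin (illustration).** Let k be the number of the 24 completers who come from the run-in, and d the run-in dropout after Session 2. The sub-study states neither. I take d from 0 to 0.30, the upper value borrowed from the main protocol's Power paragraph.

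- Subjects scheduled for a Session 2 dose = k/(1 − d)
- Total scheduled doses = k/(1 − d) + k

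| k | d = 0: subjects, doses | d = 0.30: subjects, doses |
|---|---|---|
| 0 | 0, 0 | 0, 0 |
| 6 | 6, 12 | 6/0.70 = 8.6, 14.6 |
| 12 | 12, 24 | 12/0.70 = 17.1, 29.1 |
| 24 | 24, 48 | 24/0.70 = 34.3, 58.3 |

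Because the 24 are completers, 24 is not a ceiling on subjects dosed. The k = 24 row is an extreme, since section IV.E presents the run-in as a fallback for low enrollment from the main trial. These counts cover all nitroglycerin doses, not doses to users of interacting drugs; the documents give no rate of such use.

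**The case against.** The strongest reply is that the argument rests on silence in a list that is plainly abridged. It is introduced as giving the major criteria only. It also leaves out the 2.8–5.5 mg/dL phosphorus range, the bar on existing phosphate binders and the albumin threshold, and nobody would suppose binder users were meant to enter a binder-versus-placebo balance study. The run-in is meant to mimic the main trial. The operating procedure that governs nitroglycerin is not in the file, and the summary of it in section IV.B is itself incomplete, since section IV.D(a) adds a limit. Several other rules (vitamin D analogues, immune suppressants, stable regimens, statins) require a drug history, so staff would know what each subject takes.

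Much of this stands. The omission is more likely an oversight than a decision to enroll such users, a safeguard may exist outside the file, and medications are probably reviewed at screening. But a drug history is not a rule about what to do with it, and no sentence carries exclusion 9 across. The main protocol's list is also introduced as the major criteria, and it includes the item.

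A second objection is that exclusion is heavier than necessary: EID is a control measure for interpreting FMD, so withholding the dose removes the hazard without losing the subject. That is a fair preference. The dosing-day check would close the gap by itself.

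**Conclusion.** The concern holds as a gap in the written sub-study protocol: nitroglycerin is scheduled twice for run-in subjects, and no stated rule withholds it from users of interacting drugs. It should be corrected. The conclusion concerns stated rules only; it does not show that anyone was endangered, and sight of the Standard Operating Procedure could settle it.

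No probability of harm can be given. The dose counts depend on an assumed run-in share and a borrowed dropout rate, and serve only to show that the exposure could range from none to several dozen doses.

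**What to change.** 1. **Sub-study section IV.B:** restore the main protocol's exclusion 9 in its existing wording, applied at Session 1 to run-in candidates. A user identified then, or at Session 2 before dosing, is neither dosed nor randomized.
2. **Sub-study section IV.D(a), risk paragraph:** add to the conditions for withholding nitroglycerin current use of any drug that interacts with it, sildenafil being the example, verified on the day of each dose. A subject who starts such a drug after randomization skips EID at that session, keeps FMD and stays in the study.
3. **If the Standard Operating Procedure already requires this check,** say so in both sections.

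The cost is one amendment to the sub-study, none to the main protocol, and a short medication check at Session 1 and on dosing days. A few run-in candidates may be excluded, or a few EID readings missed. The primary outcome, phosphorus balance, does not use EID, so sample size, endpoints and analysis are unaffected.

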Experimental Design (Figure 1). A 12-week randomized, placebo-controlled, double-blind design study with lanthanum (starting dose of 1,500-3,000 mg/day according to baseline serum phosphorus; up-titrated monthly as needed based on serum phosphorus) will be conducted. After providing informed consent, subjects will undergo screening prior to study start. Subjects who meet inclusion criteria will have baseline measurements performed as described below. Measurements will be made under supine, overnight fasted (water only) conditions. Patients will then be randomly assigned to receive either lanthanum or placebo (see dosing below). Allocation to the active drug versus placebo group will be random, and a stratification process will be used on the basis of baseline FMD_{BA} of <4% and $\geq 4\%$ to protect against a baseline imbalance that would not

be well handled by other statistical procedures. With counseling and adherence monitoring from a nurse, subjects will maintain their baseline diet throughout the study, including intake of phosphate of <1,000 mg/day. Measurements will then be repeated after 12 weeks. The investigators involved in the acquisition and analysis of key outcomes will be blinded to the treatment assignment of the subjects as well as serum phosphorus levels.

Figure 1:

Subjects will come to the lab at the UPI Building on 9 separate occasions:

- **Session 1:** Screening measurements, complete 3 day diet record
- **Session 2:** Baseline measurements
 - Resting arterial blood pressure and blood sampling of circulating markers (see below)
 - Venous endothelial cell collection (for subsequent protein measurements)
 - FMD_{BA} (endothelium-dependent dilation) and aortic PWV (arterial stiffness), with and without acute inhibition of oxidative stress via systemic i.v. infusion of ascorbic acid [vitamin C])
 - Endothelium-independent dilation (EID) to sublingual nitroglycerin
 - Begin study treatment (lanthanum or placebo)
- **Sessions 3-8:** Weekly/monthly check-in (see below)
- **Session 9:** Identical to Session 2 (note: subjects will not take a dose the a.m. prior to testing session)
 - **Subjects will also complete a second 3 day diet record**

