To ensure adequate enrollment, we will also recruit patients with stage IIIb and IV CKD with normal or modestly elevated serum phosphorus (2.8-5.5 mg/dL) who are *not* currently participating in the parent Phosphorus Lowering RCT (COMIRB 13-0328). Similar to the Phosphorus Lowering RCT, these patients will follow a low phosphorus diet and will be randomized to lanthanum carbonate or placebo for 12 weeks (run-in period) prior to beginning the current Phosphorus Balance protocol.

Hypothesis A. Subjects with stages IIIb and IV CKD and normal or modestly elevated serum phosphorus (2.8-5.5 mg/dL) who are treated with 12 weeks of lanthanum carbonate and a low phosphorus diet will be in negative phosphorus balance compared to subjects treated with placebo.

Hypothesis B.

Improvements in EDD will correlate with negative phosphorus balance.

Aim A. To determine phosphorus balance in subjects with stage IIIb or IV CKD after being treated with lanthanum carbonate and a low phosphorus diet or placebo and a low phosphorus diet for 12 weeks.

Aim B. To determine whether phosphorus balance in each treatment group correlates with the FMD_{BA} measurement performed at the end of the proposed Phosphorus Balance protocol.

II. Background and Significance:

Risk of cardiovascular diseases (CVD) is significantly elevated in patients with chronic kidney disease (CKD); however, the increased cardiovascular risk in this patient population is only partially explained by traditional cardiovascular risk factors.¹⁻⁶ In earlier stages of CKD, serum phosphorus levels are maintained within the normal range by up-regulating fibroblast growth factor 23 and a consequent increase in the fractional excretion of phosphorus by the kidney.¹⁰⁻¹³ However, elevated serum phosphorus even within the normal range, as is the typical case in CKD patients not requiring chronic hemodialysis, has emerged within the last decade as a novel, independent predictor of CVD risk and associated mortality.¹³⁻¹⁵ Furthermore, little is known about phosphorus balance and its association with outcomes in CKD.

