A. Outcome Measure(s): The proposed investigation is an extension of a 12-week prospective, randomized, placebo-controlled double-blind trial (Phosphorus Lowering RCT) of 60 subjects that assesses the effects of the phosphate binder, lanthanum carbonate, and a low phosphorus diet in stage IIIb and IV CKD with normal or modestly elevated serum phosphorus (2.8-5.5 mg/dL) on vascular endothelial function and arterial stiffness. Vascular endothelial function is assessed as endothelium-dependent dilation via FMD_{BA}. Subjects with stage IIIb and IV CKD with normal or modestly elevated serum phosphorus (2.8-5.5 mg/dL) who are *not* participating in the Phosphorus Lowering RCT will also be enrolled and will be treated with either lanthanum carbonate or placebo and a low phosphorus diet for a 12-week run-in period prior to initiating the current Phosphorus Balance protocol in order to mimic the parent Phosphorus Lowering RCT. After completion of 12 weeks of either lanthanum carbonate and a low phosphorus diet or placebo and a low phosphorus diet, 24 research subjects (12 treated with lanthanum carbonate and 12 treated with placebo) will participate in the proposed Phosphorus Balance Study. The primary outcome is the difference in phosphorus balance between the active and placebo groups. Serum phosphorus is not expected to change during the current Phosphorus Balance protocol as subjects will remain on the same dose of active drug or placebo that they were on during either the parent Phosphorus Lowering RCT or the 12-week lanthanum carbonate or placebo run-in period. The dose of active drug or placebo was titrated during the first month of the parent Phosphorus Lowering RCT or the 12-week run-in period and is expected to be stable during months 2 and 3 of both the parent RCT and 12-week run-in period as well as during the current Phosphorus Balance protocol. Secondary outcomes include whether there is a difference in FMD_{BA} between the active and placebo groups and whether this correlates with a difference in phosphorus balance between the active and placebo groups.

B. Description of Population to be Enrolled:

Subjects. A group of 24 subjects who have completed the 12-week parent Phosphorus Lowering RCT or the 12-week run-in period described above will provide written informed consent and serve as subjects for the current Phosphorus Balance protocol. Major inclusion/exclusion criteria are presented below:

Inclusion Criteria:

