Experimental Design. After completing the 12-week Phosphorus Lowering RCT (Figure 1) or 12-week run-in period (Figure 2), a group of 24 research subjects will complete an additional 9-day Phosphorus Balance study. Subjects will provide informed consent for the proposed Balance study. Of note, all research subjects will have an FMD_{BA} measurement at the beginning and end of the parent RCT or the 12-week run-in period. Subjects will continue taking their current dose of active drug (lanthanum carbonate) or placebo from the parent RCT or the 12-week run-in period and will begin a CTRC-prepared fixed low phosphorus diet (daily breakfast, lunch, dinner, and a snack) and will be instructed to consume only deionized water, which will be provided. They will also take polyethylene glycol 1 g with each meal (totaling 3g/day) as a non-absorbable stool marker. After 7 days, subjects will be admitted to the CTRC for a 48-hour admission.

For subjects recruited from the parent Phosphorus Lowering RCT:

- **Session 1:** Recruitment and Consent
 - All subjects currently participating in the parent Phosphorus Lowering RCT will be eligible to participate in the current Phosphorus Balance protocol
- **Session 2:** Beginning of proposed Phosphorus Balance study
 - Blood sampling to monitor serum phosphorus concentration, serum creatinine for measurement of kidney function, and evaluation of markers of mineral metabolism
 - Receive CTRC-prepared fixed low phosphorus diet (daily breakfast, lunch, dinner, and a snack) including deionized water
 - Mifflin St. Joeur equation and activity factor of 1.4 will be used to determine caloric needs. Based on their caloric needs, subjects will be assigned to one of four kilocalorie diet categories: 2000-2300, 2300-2600, 2600-2900, 2900-3200. The subjects will then select their meals from four different pre-set menus.
 - Macronutrients: 15% protein/ 30% fat/ 55% CHO \pm 2% for each macro
 - The diets will contain the same proportion of plant and meat/dairy proteins to control for the different rates of absorption of phosphorus from plant sources versus phosphorus from meat/dairy sources
 - Micronutrients controlled: phosphorus $< 1000 \pm 50$ mg/day and calcium $< 800 \pm 50$ mg/day
 - Each of the 4 kilocalorie group diets will be frozen and sent for exact measurement of phosphorus and calcium content. Subjects will be required to pick-up food in 3-day increments to prevent spoilage
 - Continue current dose of lanthanum or placebo

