We hypothesize that subjects treated with lanthanum carbonate will be in negative phosphorus balance compared to subjects treated with placebo. In addition, we expect that improvements in EDD will correlate with a negative phosphorus balance. An N = 12 from each group will be entered into the balance study (total N = 24). We will compare phosphorus balance between the two groups using an Independent Samples T-test. Data published previously²⁶ demonstrated that phosphorus balance was achieved on oral calcium carbonate vs. placebo (phosphorous balance of 153 vs. 95 mg/d with a SD = 82); however, the sample size of 8 in a crossover design was not enough to conclude equivalence. We propose to use N = 12 per group, which will give a two group 0.050 two-sided t-test 81.3% power with a standard deviation of 43. The results of the current protocol will be used to aid in the interpretation of the parent Phosphorus Lowering RCT. Pearson correlation coefficients will be used to determine the correlation between phosphorus balance and FMD_{BA} at the end of the 9-day diet intervention (i.e., the end of the current protocol) in each treatment group.

G. Summarize Knowledge to be Gained:

The findings from the proposed research should provide important new information regarding phosphorus balance in CKD and its effect on vascular function in this population of patients subject to a high degree of CVD morbidity and mortality. No phosphorus balance study in CKD patients treated with a non-calcium-containing phosphate binder, such as lanthanum carbonate, has ever been conducted. Moreover, the length of time subjects will be treated with active or placebo drug prior to balance measurements and the numerous measurements of stool and fecal phosphorus exceeds that of other studies. Together, this information will provide important insight into phosphorus metabolism and vascular function in CKD.

H. References:

1. [name] J, Chonchol MB. Nontraditional risk factors for cardiovascular disease in patients with chronic kidney disease. *Nat Clin Pract Nephrol*. 2008;4:672-681.

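### The sub-study's Hypothesis B is about improvement in EDD, but the only planned correlation uses end-of-protocol FMD and omits the pre-treatment value, so it is only indirect evidence

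*Combined protocol and SAP*

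**What the plan says.** All places are in the sub-study protocol unless stated.

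- Section I, Hypothesis B: "Improvements in EDD will correlate with negative phosphorus balance". Section IV.F repeats it: "we expect that improvements in EDD will correlate with a negative phosphorus balance".
- Section I, Aim B: "To determine whether phosphorus balance in each treatment group correlates with the" FMD value taken when the balance protocol ends.
- Section IV.A, secondary outcomes: whether FMD differs between the arms "and whether this correlates with a difference in phosphorus balance between the active and placebo groups". No change from baseline is named.
- Section IV.F, the only planned statistic: "Pearson correlation coefficients will be used to determine the correlation between phosphorus balance and" FMD "at the end of the 9-day diet intervention (i.e., the end of the current protocol) in each treatment group".
- Section IV.C: every subject has an FMD "measurement at the beginning and end of the parent RCT or the 12-week run-in period", and a final FMD follows at the end of the balance protocol.
- Main protocol, section IV.A: the parent trial's primary outcomes are changes from baseline to week 12 in FMD and aPWV.

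**The concern.** Improvement means change, and the planned statistic contains no change. Subjects differ in FMD before they take any tablet, and that difference carries into the end value. A correlation of balance with end-level FMD therefore reflects both where a subject started and how the subject responded. A reader of the result could not separate the two. Section IV.F says the sub-study is to help interpret the parent trial, which measures FMD as change, so the two would not be on the same footing. The level, change and baseline-adjusted correlations can also differ, and nothing pre-stated would prevent choosing among them after the data are seen.

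**Working it through.** **No figure to reproduce.** The documents give no power, sample size or expected correlation for Aim B. The 81.3% in section IV.F belongs to the t-test on balance.

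**Inputs.** From section IV.F: n = 12 per arm. Two-sided 0.05 is stated there for the t-test and assumed here for the correlation. Not in the documents and therefore assumed: ρ, the correlation of pre-treatment with end FMD (0.3 to 0.9); b, the correlation of balance with pre-treatment FMD; equal FMD variance at both times. Hypothesis B predicts a negative correlation.

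**1. Balance unrelated to baseline FMD (b = 0).** End-level r divided by r with change is √(2(1−ρ)). End-level r divided by the baseline-adjusted r is √(1−ρ²).

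| ρ | against change | against adjusted |
|---|---|---|
| 0.3 | 1.18 | 0.95 |
| 0.5 | 1.00 | 0.87 |
| 0.7 | 0.77 | 0.71 |
| 0.9 | 0.45 | 0.44 |

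The sign is right throughout. Against raw change there is no dilution at ρ of 0.5 or less.

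**2. Balance related to observed baseline FMD, but not to response given that baseline.** End-level r = bρ. r with change = −b√((1−ρ)/2). Adjusted r = 0. For b = −0.5, with rejection rates simulated in 100,000 arms of 12:

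| ρ | end-level r | r with change | end-level test rejects | change test rejects | adjusted test rejects |
|---|---|---|---|---|---|
| 0.3 | −0.15 | +0.30 | 7% | 15% | 5% |
| 0.5 | −0.25 | +0.25 | 12% | 12% | 5% |
| 0.7 | −0.35 | +0.19 | 21% | 9% | 5% |
| 0.9 | −0.45 | +0.11 | 32% | 6% | 5% |

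For b = −0.3 the end-level r runs from −0.09 to −0.27 and its test rejects in 6% to 14% of arms.

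**3. Balance related to a stable vessel trait that each FMD measures with error, and unrelated to change.** End-level r = b. r with change = 0. Adjusted r = b√((1−ρ)/(1+ρ))/√(1−b²). Example at b = −0.5 and ρ = 0.5: −0.5 × 0.577/0.866 = −0.33.

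| ρ | adjusted r | adjusted test rejects | change test rejects | end-level test rejects |
|---|---|---|---|---|
| 0.3 | −0.42 | 26% | 5% | 40% |
| 0.5 | −0.33 | 17% | 5% | 40% |
| 0.7 | −0.24 | 11% | 5% | 40% |
| 0.9 | −0.13 | 7% | 5% | 40% |

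**4. Precision in one arm.** Critical |r| = t/√(df + t²). With df = 10, 2.228/√(10 + 4.964) = 0.576. With df = 9 (one covariate), 2.262/√(9 + 5.117) = 0.602. Fisher-z power at r = 0.5, where atanh(0.5) = 0.549: unadjusted, 0.549 × √9 = 1.648 and Φ(1.648 − 1.960) = 38%; adjusted, 0.549 × √8 = 1.554 and Φ(1.554 − 1.960) = 34%. The r needed for 80% power is 0.73 unadjusted and 0.76 adjusted. A correlation with change has the same 10 df as the planned one.

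**The case against.** The strongest reply is that the plan is mostly consistent at the level of FMD. The key secondary goal in section I speaks of vascular function as measured by FMD, and Aim B and section IV.F's statistic use the end value. Only the hypothesis wording speaks of improvement, so rewording Hypothesis B would remove the contradiction. That is fair as far as it goes, and end-level FMD is relevant to that goal. But section IV.F restates the hypothesis as improvement beside the statistic meant to test it, and rewording would leave an available baseline value unused.

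It can also be said that the illustrations rest on assumed b and ρ, and that nothing in the documents suggests b = −0.5. This stands. With b = +0.5 and ρ = 0.5 in step 2 the signs reverse: end-level r is +0.25, which looks like evidence against the hypothesis, and r with change is −0.25, which looks like support.

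Three stronger readings are tempting and are not supported:

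- A reader might infer that the planned correlation is invalid or has the wrong sign. Step 1 shows that it need not be distorted at all against change, and the documents do not give the quantities that would settle the matter.
- A reader might infer that baseline adjustment is the one correct analysis. Hypothesis B names improvement, which is change. Step 3 shows that the adjusted test can exceed 5%, and step 2 shows that the change test can too.
- A reader might infer that pre-treatment FMD goes to waste. It is unused only in the sub-study; the parent trial uses it for its own primary outcome.

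**Conclusion.** The mismatch is real and can be read directly from the text. The planned end-level correlation is indirect evidence on Hypothesis B. The size and direction of any distortion depend on two correlations that the documents do not give, so only conditional figures are possible. With no true relation to response and an assumed b of −0.5, the end-level test rejects in 7% to 32% of arms under one model and 40% under the other. On the same assumptions neither alternative is protected in every case: the change test reaches 6% to 15% when balance follows observed baseline only, and the adjusted test 7% to 26% when balance follows a stable trait measured with error. This is a secondary analysis with 12 per arm, no power claim and low power whichever form is used. The primary comparison of phosphorus balance is unaffected. The correction is a cheap improvement.

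**What to change.** Align Hypothesis B, Aim B, the secondary outcome in section IV.A and the analysis plan in section IV.F on the following, in each arm:

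1. **Hypothesis B analysis:** the correlation of phosphorus balance with change in FMD, with its 95% CI. Name the endpoints, since FMD is taken at three times: from pre-treatment (start of the parent trial or run-in) to the end of the balance protocol. Main protocol section IV.C measures FMD "with and without acute inhibition of oxidative stress via systemic i.v. infusion of ascorbic acid", so for parent-trial subjects specify the value without ascorbic acid. State one scale, mm or %, because section IV.D of the sub-study gives both.
2. **Pre-stated alongside:** the association of balance with end-of-protocol FMD adjusted for pre-treatment FMD, as a partial correlation or slope with its 95% CI.
3. **Descriptive:** the end-level Pearson correlation already planned.

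Add a sentence saying that the change and adjusted results can disagree, that neither holds its level in every case, and that balance is observed and not randomised, so neither association is causal.

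The cost is wording only, with no new measurement. The change correlation uses no extra degree of freedom. The adjusted model uses one per arm, which takes power at r = 0.5 from about 38% to about 34% if the correlation itself is unchanged.
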